13.8.3. Key Secondary Analyses

If the primary efficacy analysis is statistically significant ($p < 0.05$), then additional confirmatory tests using the ITT population will be performed in the following prespecified order:

- Proportion of patients in clinical remission at Week 8: 0.5 mg dose versus placebo
- Proportion of patients in clinical response at Week 8: 1 mg dose versus placebo
- Proportion of patients in clinical response at Week 8: 0.5 mg dose versus placebo
- Change in Mayo score from baseline at Week 8: 1 mg dose versus placebo
- Change in Mayo score from baseline at Week 8: 0.5 mg dose versus placebo
- Proportion of patients with mucosal healing at Week 8: 1 mg dose versus placebo
- Proportion of patients with mucosal healing at Week 8: 0.5 mg dose versus placebo
- Proportion of patients in clinical remission at Week 32: 1 mg dose versus placebo
- Proportion of patients in clinical remission at Week 32: 0.5 mg dose versus placebo
- Proportion of patients in clinical response at Week 32: 1 mg dose versus placebo
- Proportion of patients in clinical response at Week 32: 0.5 mg dose versus placebo
- Change in Mayo score from baseline at Week 32: 1 mg dose versus placebo
- Change in Mayo score from baseline at Week 32: 0.5 mg dose versus placebo
- Proportion of patients with mucosal healing at Week 32: 1 mg dose versus placebo
- Proportion of patients with mucosal healing at Week 32: 0.5 mg dose versus placebo

Provided that all previously specified tests are statistically significant ($p < 0.05$), each of these comparisons will be assessed using a two-sided test at the $\alpha = 0.05$ level of significance.

However, if a comparison is not statistically significant, then all subsequent comparisons will be considered exploratory.

Secondary endpoints that are defined as proportions will be analyzed using the same type of methodology as described for the primary analysis. Analyses of all proportion endpoints using the CMH test will be completed using the data from the two groups being compared. Quantitative secondary endpoints will be analyzed using analysis of covariance (ANCOVA) models with effects for treatment group (three levels) and prior anti-TNF therapy experience, and with the baseline value of the corresponding endpoint included as a covariate. All secondary analyses will be carried out using two-sided test at the 5% level of significance.

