13.11. Missing Data

For the primary analysis, as well as for the analyses of all key secondary efficacy endpoints that are defined as proportions, patients who do not provide data at the specified time point will be classified as nonresponders.

The Mayo score used for clinical endpoints in the study will utilize the Mayo endoscopy score derived from the central reader. In the case that a central endoscopic result is missing and the endoscopic subscore read by the Investigator will be utilized.

One of the key secondary efficacy endpoints (change in Mayo score) is a quantitative endpoint. For the key secondary analyses of this variable, missing values will be replaced by the least favorable observed change observed in the placebo group.

Sensitivity analyses of the primary and key secondary endpoints will be carried out to investigate the impact of missing data on the efficacy conclusions. These will include analyses of completed cases, observed cases, and multiple imputation model-based methods.

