3.1.3. Exploratory Objectives

3.2. Endpoints

3.2.1. Efficacy Endpoints

Primary Efficacy Endpoint:

[figure not shown]
• The primary endpoint is the proportion of patients in clinical remission at Week 8, defined as a Mayo score of ≤ 2 points and with no individual subscore of > 1 point

Key Secondary Efficacy Endpoints (rank ordered):

- Proportion of patients with a clinical response at Week 8, defined as a reduction from baseline in Mayo score of ≥ 3 points and ≥ 30%, and a decrease from baseline in the rectal bleeding subscore of ≥ 1 point or an absolute rectal bleeding subscore of ≤ 1 point
- Change from baseline in Mayo score at Week 8
- Proportion of patients with mucosal healing at Week 8, defined by an endoscopy subscore of ≤ 1
 point

Other Secondary Efficacy Endpoints:

- Proportion of patients in clinical remission at Week 32 defined as Mayo score of ≤ 2 points with no individual subscore of > 1 point
- Proportion of patients with a clinical response at Week 32, defined as a reduction from baseline in Mayo score of ≥ 3 points and ≥ 30%, and a decrease from baseline in the rectal bleeding subscore of ≥ 1 point or an absolute rectal bleeding subscore of ≤ 1 point
- Proportion of patients with mucosal healing at Week 32, defined by an endoscopy subscore of ≤ 1 point

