5.1. Time Point Definitions

Study Day for Induction and Maintenance Periods

All visit data will be assigned a study day, from the Visit 1 in the Induction Period according to the following rules:

- Visit 1 Day will be designated as Day 1
- All other days after Day 1: Study Day = (Visit Date Visit 1 Date + 1)
- All other days before Day 1: Study Day = (Visit Date Visit 1 Date)

Study days for evaluations occurring during the Screening visit will be negative numbers (e.g., "-7"), no Day 0 is defined for this study.

Study Day for the Open Label Period

All visit data will be assigned a study day, from the Visit 1 in the Open Label Period according to the following rules:

- OLP Day 1 will be designated as Day 1
- All other days after OLP Day 1: Open Label Day = (Visit Date Open Label Visit 1 Date + 1)
- All other days before OLP Day 1: Open Label Day = (Visit Date Open Label Visit 1 Date)

Baseline Measurement

There will be two baseline definitions:

Baseline: The latest assessments completed prior to initial study drug administration will be used as the Baseline measurement for all analyses for the IP and MP. It will also be used as the Baseline measurement for efficacy analyses for the OLP.

Treatment Baseline: The last assessment prior to initial administration of RPC1063 will be used as the Baseline measurement for safety analyses for the OLP.

Visits

Visits identifiers on the study electronic case report forms (eCRFs) will be used.

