5.2.2. Mayo Score

The Mayo score is a standardized, accepted, numerical scale used to evaluate disease severity in people with UC.

The Mayo score consists of four subscores, each ranging from (0-3) for a total score that ranges from 0 to 12:

- 1. Stool frequency^a
 - 0=Normal number of stools for this patient
 - 1 = 1 to 2 stools more than normal
 - 2=3 to 4 stools more than normal
 - 3=5 or more stools more than normal
- 2. Rectal bleeding^b
 - 0=No blood seen
 - 1 = Streaks of blood with stool less than half the time
 - 2=Obvious blood with stool most of the time
 - 3 = Blood alone passes
- 3. Findings on endoscopy
 - 0=Normal or inactive disease
 - 1 = Mild disease (erythema, decreased vascular pattern, mild friability)
 - 2 = Moderate disease (marked erythema, lack of vascular pattern, friability, erosions)
 - 3 = Severe disease (spontaneous bleeding, ulceration)
- 4. Physician's global assessment^c
 - 0 = Normal
 - 1 = Mild disease
 - 2 = Moderate disease
 - 3 = Severe disease

- ^a Each patient serves as his or her own control to establish the degree of abnormality of the stool frequency.
- ^b The daily bleeding score represents the most severe bleeding of the day.
- ^c The physician's global assessment acknowledges the three other criteria, the patient's daily recollection of abdominal discomfort and general sense of well-being, and other observations, such as physical findings and the patient's performance status.

The Mayo score will be derived at all visits when an endoscopy is performed. For these visits, the Mayo score will be derived using the endoscopy subscore and the non-endoscopy subscores performed at the same nominal visits, even if the assessments have different dates. The baseline Mayo score will be derived from the most recent endoscopy subscore (Item 3) completed during Screening and the last non-missing non-endoscopy subscores (i.e., Items 1, 2, and 4) prior to initial study drug administration.

Partial Mayo scores are calculated using data from Items 1, 2, and 4 only.

Mayo scores are calculated using:

- 1. The stool frequency and rectal bleeding data form the most recent consecutive 3-day period prior to the visit, excluding the following:
 - a. The day medications for constipation, diarrhea, or bowel irregularity are taken
 - b. The day(s) of a procedure or preparation for a procedure (e.g., enemas, other laxative, clear liquid diet) that would affect bowel frequency or blood content of the stool

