6.1. General Analysis Approach

Unless otherwise noted, all summaries of data by treatment group during the IP/MP and the OLP will include the following three groups:

- 1) Placebo
- 2) RPC1063 0.5 mg
- 3) RPC1063 1.0 mg

The following conventions will be used for all data presentations and analyses unless otherwise specified.

- Appropriate descriptive statistics will be computed and displayed (by time point and other key variables as appropriate) for both continuous and categorical variables. For continuous variables, descriptive statistics will include n (the number of patients with non-missing data), mean, standard deviation (SD), median, and minimum and maximum values. For categorical data, the number and percentage of patients within each category will be presented. The denominator for percentages will be based on the number of patients with non-missing data appropriate for summary purposes. Unless otherwise noted, all percentages will be presented to one decimal place.
- Individual data listings of all data represented on the eCRF and from the clinical laboratory will be presented. Sort order for data listings will be treatment, site-patient number, visit, and assessment period where appropriate.
- Version 9.1 (or higher) of the SAS® statistical software package will be used to provide all tables, figures, data listings, and analyses.

• There are approximately 70 study sites in this study. Due to the large number of study sites and the small numbers of patients per site, the analysis of efficacy endpoints will not include adjustments for study site.

Further analysis and reporting conventions are described in Section 7.

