6.4. Missing values

The Mayo score used for clinical endpoints in the study will utilize the Mayo endoscopy score derived from the central reader. In the case that a central endoscopic result is missing the endoscopic subscore read by the Investigator will be utilized.

For calculation of the Mayo score for the efficacy endpoints, at least 2 of the 4 subscores must be available to calculate the total Mayo score. A missing subscore(s) will be carried forward from the most recent previous visit for which the subscore is available. The endoscopy subscore is not considered missing if the Investigator endoscopic subscore is available. If more than 2 subscores are missing, then the Mayo score will be considered missing.

For calculation of the partial Mayo score for the efficacy endpoints, at least 2 of the 3 subscores must be available to calculate the partial Mayo score. The missing subscore will be carried forward from the previous visit. If more than 1 subscore is missing, then the partial Mayo score will be considered missing.

For the primary analysis, as well as for the analyses of all key secondary efficacy endpoints that are defined as proportions, patients who have missing Mayo or partial Mayo scores at the specified time point will be classified as nonresponders.

One of the key secondary efficacy endpoints (change in Mayo score) is a quantitative endpoint. For the key secondary analysis of this variable, missing values will be replaced by the last observation carried forward (LOCF). If no post-Baseline observation is available to carry forward, then the average score for the observed values within the same treatment group will be used, rounded to the nearest integer.

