6.19.6. Other Efficacy Analyses

6.19.6.1. Mayo Score at Week **32**

The analyses will be performed for all available Week32 data at the time of database lock as described in Section 6.10.

- Proportion of patients in clinical remission at Week 32
- Proportion of patients in clinical response at Week 32
- Change in Mayo score from baseline at Week 32
- Proportion of patients with mucosal healing at Week 32

The endpoints that are defined as proportions will be analyzed using the same type of methodology as described for the primary analysis. Analyses of all proportion endpoints using the CMH test will be completed using the data from the two groups being compared. Quantitative secondary endpoints such as change in Mayo score will be analyzed using ANCOVA models with effects for treatment group and prior anti-TNF therapy experience, and with the baseline value of the corresponding endpoint included as a covariate. All analyses will be carried out using two-sided test at the 5% level of significance.

Actual and change from baseline in partial Mayo scores over time will be plotted.

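### SAP 6.19.6.1 gives no rule for patients without a Week 32 Mayo score on assigned treatment; the protocol keeps them in an ITT test with a penalised value, and SAP section 8 does not list the difference

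*SAP*

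**What the plan says.** **Protocol.** Section 13.8.3 places the Week 32 endpoints in the ordered confirmatory tests on the ITT population, including "Change in Mayo score from baseline at Week 32: 1 mg dose versus placebo" and the same test for 0.5 mg. For the key secondary analyses of change in Mayo score, section 13.11 states that "missing values will be replaced by the least favorable observed change observed in the placebo group".

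**SAP.** Section 3.2.1 limits the key secondary endpoints to Week 8 and puts Week 32 remission, response and mucosal healing under "Other Secondary Efficacy Endpoints". The Week 32 change in Mayo score is in neither list, but section 6.19.6.1 analyses it by ANCOVA: "The analyses will be performed for all available Week32 data at the time of database lock". That sentence goes on to refer to section 6.10, which describes the lock for the primary analysis.

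The SAP's imputation rule for this variable is in section 6.4: "For the key secondary analysis of this variable, missing values will be replaced by the last observation carried forward (LOCF". The treatment-failure rule in section 6.19 is triggered by prohibited changes in UC medication, by colectomy or ostomy, and by stopping for lack of effect before Week 8. Relapse in Maintenance and entry to the open-label period (OLP) are not triggers.

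SAP section 8 lists two departures from the protocol: histologic remission and plasma protein biomarkers.

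**The concern.** Two groups normally have no Week 32 Mayo score on assigned treatment. Week 8 non-responders never enter Maintenance (protocol 9.1). Maintenance responders who relapse may move to open-label 1 mg and then follow the OLP schedule. An ANCOVA with no imputation rule omits anyone without an outcome value.

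Week 8 non-response and relapse are outcomes that the drug is meant to change. Dropping these patients conditions the comparison on events after randomization, so it no longer compares the arms as randomized. The protocol analysis counts the same patients as poor outcomes. The two analyses answer different questions, can disagree on the same data, and neither document says which governs.

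**Working it through.** **1. The plan's own figure.** The documents give no effect size or power for the Week 32 change. Their only powered comparison is Week 8 remission, 10% vs 31% at 60 per arm. The pooled two-proportion formula gives 82.1% power at 31% and 78.9% at 30%, so 21 points is the smallest whole-point difference with at least 80% power. Only the 60 per arm is used below.

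**2. Does another SAP rule fill the gap?**
- *Carry-forward of the total score (6.4)* is for the key secondary analysis, which 3.2.1 confines to Week 8.
- *Carry-forward of subscores (6.4)* needs at least 2 of 4 subscores. A patient with no Week 32 visit has none.
- *Treatment failure (6.19)* catches a relapser with, for example, a steroid increase for UC or a new immunosuppressant. It does not catch relapse or OLP entry as such.
- *Relapse-visit score.* By SAP 5.2.2, "The Mayo score will be derived at all visits when an endoscopy is performed", so a relapser may have one. By SAP 5.1, "Visits identifiers on the study electronic case report forms (eCRFs) will be used", so it would not normally carry the Week 32 label. The eCRF labels themselves are not in the documents.

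**3. The ordered tests.** Protocol 13.8.3 lists 15 tests after the primary. Eight are at Week 32 (four endpoints at two doses), two of them for change in Mayo score. SAP 6.19.3 lists 6, none at Week 32.

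**4. Size for change in Mayo score (assumptions, not document figures).** Take 60 per arm, with 33 Week 8 responders on 1 mg and 18 on placebo. Relapsers (1 mg/placebo) are 3/3, 6/6, 6/9 or 3/9. Continuing responders have the same mean change m in both arms, -4 or -6. The least favorable placebo change L is 0, +1 or +3.

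With c = responders minus relapsers, each arm mean under the protocol rule is [c·m + (60 - c)·L]/60. The difference is therefore (c1 - c0)/60 × (m - L). The available-data difference is 0 by construction.

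| Relapsers | c1 - c0 | m = -4; L = 0, +1, +3 | m = -6; L = 0, +1, +3 | Share from Week 8 gap |
|---|---|---|---|---|
| 3/3 or 6/6 | 15 | -1.00, -1.25, -1.75 | -1.50, -1.75, -2.25 | 15/15 = 100% |
| 6/9 | 18 | -1.20, -1.50, -2.10 | -1.80, -2.10, -2.70 | 15/18 = 83% |
| 3/9 | 21 | -1.40, -1.75, -2.45 | -2.10, -2.45, -3.15 | 15/21 = 71% |

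The relapse part alone is 0 with equal relapse counts, 3/60 × (m - L) = -0.20 to -0.45 for 6/9, and 6/60 × (m - L) = -0.40 to -0.90 for 3/9.

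**5. A second illustration.** A simulation (2,000 runs, t-test) assumed Week 8 response of 55% vs 35%, relapse among responders of 20% on active, and 20%, 40% or 60% on placebo.
- Available data: about 26 active patients against 17, 13 or 8 placebo patients, with a difference of about 0.
- Protocol rule: 60 vs 60, with differences of -0.56, -0.72 and -0.85.
- Carry-forward from Week 8: about -0.85 whatever the relapse rate.
- Equal response (35% each), protocol rule: about 0, -0.2 and -0.4.

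These differences are smaller than in step 4 because L was drawn from placebo patients with a Week 32 score, who are all continuing responders. In the first case the expected completer gap is (0.55 - 0.35) × 0.8 = 0.16, so m - L = -0.56/0.16 = -3.5. With m near -5, L is about -1.5, which is still an improvement.

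**6. Proportions, only if the nonresponder rule does not carry over.** With relapsers 6/9 and response in 18 of 27 and 6 of 9 continuing patients, the protocol rule gives 18/60 = 30.0% vs 6/60 = 10.0%. For CMH with two equal strata, the summed deviation is 6 and the variance is 2 × 30·30·12·48/(60²·59) = 4.88. Chi-square is 36/4.88 = 7.37, p = 0.007. Available data give 66.7% vs 66.7%.

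**The case against.** **Available may describe only the data cut.** The sentence points to section 6.10, where data after Week 8 are still accruing, and section 6.19 bases all efficacy endpoints primarily on the ITT population. A reader might infer that the SAP expressly excludes relapsers and non-responders. It does not: their omission follows from the lack of a rule. But reading the sentence as a data cut still supplies no value for them. Stretching the carry-forward rule to Week 32 would give a relapser the Week 8 responder score, unless the relapse-visit score were used. Either way it departs from protocol 13.11.

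**Sensitivity analyses may cover Week 32.** A reader might infer that none does, because SAP 6.19.5 first refers to primary and key secondary endpoints. The same section then says that the primary and secondary efficacy analyses will be repeated. That may mean only 6.19.3, but Week 32 is not clearly excluded. Even so, a sensitivity analysis does not define the main one.

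**Proportions are probably protected.** Section 6.19.6.1 applies the primary methodology, and 6.4 counts missing as nonresponse in the primary analysis. This stands as the likelier reading. It is not certain, since 6.4 words the rule for primary and key secondary endpoints and SAP 6.1 says "The denominator for percentages will be based on the number of patients with non-missing data appropriate for summary purposes".

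**The SAP may follow an earlier protocol.** Its 30-day follow-up and 20-week OLP end differ from the current protocol. A reader might infer a knowing, undeclared departure; the documents do not show one. They show that the current pair conflicts.

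**The endpoint's standing is unclear in the protocol too.** Section 8.2.1 does not list the Week 32 change as a secondary endpoint; it appears only in 13.8.3. This stands, and the SAP removes Week 32 from the ordered tests, which lowers the stakes.

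**Conclusion.** The concern holds for the Week 32 change in Mayo score. As written, the SAP compares continuing responders and the protocol compares everyone in the ITT population, and SAP section 8 discloses neither this nor the removal of Week 32 from the ordered tests. Early-termination visits may supply scores for some patients who leave, which narrows the gap but does not close it.

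The size is illustrative. It rests on assumed response and relapse rates, equal change among continuing patients, and the assumed L. The available-data result of 0 is a consequence of the second assumption, not a forecast. A reader might infer that relapse drives the difference, but in these examples most or all of it comes from the assumed Week 8 response gap. A reader might also infer from Table 1 that no endoscopy is done at relapse. The table's layout does not support that, and the relapse definition in protocol 11.1.2 itself requires an endoscopic subscore and a partial Mayo score.

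The primary endpoint and all Week 8 tests are unaffected. This is worth correcting because it changes what a secondary efficacy result means.

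**What to change.** Add to SAP 6.19.6.1:

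- Include every ITT patient who, at the data cut, has completed or would have been eligible to complete Week 32.
- Patients without a Week 32 Mayo score on assigned treatment, including Week 8 non-responders and Maintenance relapsers, are nonresponders for the proportions. For change in Mayo score they receive the protocol 13.11 least favorable placebo change, with the visit it is drawn from stated.
- As supportive analyses, show available data, and an analysis that uses the relapse-visit Mayo score for relapsers.
- In SAP section 8, list the removal of Week 32 from the ordered tests.

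If the sponsor keeps available data as the main Week 32 analysis, list that in SAP section 8 as a change from protocol 13.8.3 and 13.11, and label it descriptive.

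The cost is a few SAP sentences and no new procedure. There is a statistical price. In the step 4 scenarios 75 to 84 of 120 patients (62.5% to 70%) would receive one identical value, and the rule would differ from the SAP's carry-forward rule at Week 8. The supportive analyses should therefore be reported alongside the main one.

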6.19.6.2. Mayo Score at the End of OLP

The analyses will be carried out when all patients have completed (or would have been eligible to complete) the OLP of the study. The mayo score will be summarized using descriptive statistics.

6.19.6.3. Partial Mayo Score

Partial Mayo score at all visits will be analyzed as follows:

- Proportion of subjects in clinical remission based on the partial Mayo score at each visit through last available
- Proportion of subjects in clinical response based on the partial Mayo score at each visit through last available
- Change in partial Mayo score from baseline at each visit through last available

The endpoints that are defined as proportions will be analyzed using the same type of methodology as described for the primary analysis. Analyses of all proportion endpoints using the CMH test will be

completed using the data from the two groups being compared. Quantitative secondary endpoints such as change in Mayo score will be analyzed using ANCOVA models with effects for treatment group and prior anti-TNF therapy experience, and with the baseline value of the corresponding endpoint included as a covariate. All analyses will be carried out using two-sided test at the 5% level of significance.

